10.3.5.2. Subgroup Analyses

The following subgroups will be analyzed using the efficacy estimand to evaluate consistency of treatment effects on the primary efficacy measure if there are sufficient numbers of patients in each treatment by subgroup (for example, 10%):

- Age (<65, ≥65 years and <75, ≥75 years and <65, ≥65 to <75, ≥75 to <85, ≥85 years)
- HbA1c stratum (≤8.0%, >8.0%)
- Sex (male or female)
- BMI (<25, ≥25 kg/m² and <30, ≥30 kg/m² and <35, ≥35 kg/m²)
- Duration of diabetes (using the median as the cut-off)
- Race
- Ethnicity
- Country
- Region
- Baseline 1-hour PPG excursion
- Baseline 1-hour PPG (PPG ≤180 mg/dL, >180 mg/dL)
- Baseline 2-hour PPG excursion
- Baseline 2-hour PPG (PPG ≤180 mg/dL, >180 mg/dL)
- Prandial insulin dosing plan (carbohydrate counting, pattern adjustment)
- Type of basal insulin during the lead-in period (glargine, degludec)
- Number of prandial doses at study entry (<3, ≥3)
- SGLT-2 inhibitor treatment

Analyses for HbA1c and change from baseline in HbA1c will be performed using an MMRM model that includes the same fixed effects given for the primary analysis model plus factors of subgroup, 2-way interaction of subgroup and treatment, 2-way interaction of subgroup and visit, and 3-way interaction of treatment, visit and subgroup. The interaction of subgroup and treatment at the primary endpoint (Week 26) will be evaluated to assess the treatment by subgroup interaction. When analyzing HbA1c stratum (≤8.0%, >8.0%) as a subgroup, the baseline HbA1c will not be included as a covariate to avoid confounding.

Additional subgroup analyses may also be performed.

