5. To compare LY900014 and insulin lispro with respect to the rate of severe hypoglycemic events	5. Rate (events/patient/100 years) of severe hypoglycemic events from baseline through Week 26
6. To compare LY900014 and insulin lispro with respect to the incidence and rate of documented symptomatic postmeal hypoglycemia	6. Rate (events/patient/year and/or events/patient/30 days) and incidence (percent of patients with at least 1 event) of documented symptomatic postmeal hypoglycemia within 1 and 2 hours after start of a meal from baseline through Week 26
7. To compare LY900014 and insulin lispro with respect to the incidence and rate of documented symptomatic hypoglycemia	7. Rate (events/patient/year and/or events/patient/30 days) and incidence (percent of patients with at least 1 event) of documented symptomatic hypoglycemic events from baseline through Week 26
8. To compare LY900014 and insulin lispro with respect to 1,5-AG	8. Change from baseline 1,5-AG values at Week 26
9. To compare LY900014 and insulin lispro with respect to 10-point SMBG profiles	9. Change from baseline 10-point SMBG values at Week 26

Objectives and Endpoints

Objectives	Endpoints
Other Secondary Objectives (Continued)	
10. To compare LY900014 and insulin lispro with respect to total, basal, and prandial insulin dose	10. Change from baseline in total, basal and prandial insulin dose and prandial/total insulin dose ratio at Week 26
11. To compare LY900014 and insulin lispro with respect to diabetes treatment satisfaction as measured by the ITSQ	11. Change from baseline ITSQ regimen inconvenience and lifestyle flexibility domain scores at Week 26
12. To compare LY900014 and insulin lispro with respect to the proportion of patients achieving HbA1c targets	12. The proportion of patients with HbA1c <7% and ≤6.5% at Week 26
Tertiary/Exploratory Objectives	
13. To compare the safety of LY900014 relative to insulin lispro	13. Adverse events, vital signs, chemistry, and hematology laboratory measures
14. To compare the incidence of treatment-emergent anti-insulin lispro antibodies for LY900014 and insulin lispro	14. Incidence of treatment-emergent positive anti-insulin lispro antibodies
15. To compare LY900014 and insulin lispro with respect to quality of life as measured by the EQ-5D-5L	15. Change from baseline in EQ-5D-5L UK-population based health state index score and EQ-VAS score at Week 26

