Table 6.2. Baseline and Post-Baseline Definitions and Patient Population by Study Period and Type of Analysis

Study Period/Analysis	Patient Population	Baseline Observations	Post-Baseline Observations
Lead-In Period			
TEAEs	All Enrolled Patients	Prior to first dose of open-label insulin lispro (or Visit 2 date if the dose date is missing)	The entire lead-in period after first dose of open-label insulin lispro and prior to the first dose of IP (or Visit 8 date if the dose date is missing).
Basal, prandial, and total insulin doses, and prandial/total insulin dose ratios continuous analysis	All Randomized Patients	Visit 2	Visits 3 to 8 prior to initiation of IP
Weight MMRM and ANCOVA	All Randomized Patients	Last of Visits 1-2	Visits 3–8 AND Last of Visits 3-8
26-Week Treatment Period (including Safety Follow-Up Visit where applicable)			
HbA1c MMRM and ANCOVA (efficacy estimand)	All Randomized Patients with a baseline and at least 1 post-baseline observation while on IP	Last of Visits 7-8	Visits 11, 13, 15, and 18 prior to discontinuation of IP AND Last of Visits 9-18 prior to discontinuation of IP
HbA1c ANCOVA (ITT estimand)	All Randomized Patients with a baseline and at least 1 post-baseline observation	Last of Visits 7-8	Visit 18 with imputation for patients who discontinue study prior to Visit 18
HbA1c categorical analyses longitudinal logistic regression and LOCF logistic regression	All Randomized Patients with a baseline and at least one post-baseline observation while on IP	Last of Visits 7-8	Visits 11, 13, 15, and 18 prior to discontinuation of IP AND Last of Visits 9-18 prior to discontinuation of IP
1-hr and 2-hr PPG and other MMTT variables (efficacy estimand)	All Randomized Patients with a post-baseline observation while on IP	Visit 8 prior to initiation of IP	Visit 18 prior to discontinuation of IP
1-hr and 2-hr PPG and other MMTT variables (ITT estimand)	All Randomized Patients with a post-baseline observation	Visit 8 prior to initiation of IP	Visit 18 regardless of IP use
10-point SMBG, basal, prandial insulin doses, prandial/total insulin dose ratios	All Randomized Patients with a baseline and at least one post-baseline observation	Visit 8 prior to initiation of IP	Visits 11, 13, 15, and 18 prior to discontinuation of IP AND Last of Visits 9-18 prior to discontinuation of IP

Baseline and Post-Baseline Definitions and Patient Population by Study Period and Type of Analysis

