Subgroup analysis for the following selected efficacy and safety variables will be performed by the TEADA status during the analysis period of Visit 2 to Visit 801:

- HbA1c and change from baseline in HbA1c
- 1-hour and 2-hour PPG excursions
- basal, prandial, and total insulin dose
- treatment-emergent injection site reaction and hypersensitivity reaction
- event rate of overall hypoglycemic events

The analyses for HbA1c and change from baseline in HbA1c will be performed using an MMRM model for the primary analysis and the HbA1c data prior to permanent discontinuation

of IP. The model will include additional fixed terms of subgroup, subgroup by treatment interaction, subgroup by visit interaction, and 3-way interaction of treatment, subgroup and visit.

The PPG excursions will be analyzed by the ANCOVA model same as the model specified in Section 6.11.2 using the efficacy estimand. The model will include additional terms of subgroup, subgroup by treatment interaction, subgroup by visit interaction, and 3-way interaction of treatment, subgroup and visit.

The subgroup analysis for insulin dose will use the MMRM model specified in Section 6.11.5 using the efficacy estimand. The model will include additional fixed terms of subgroup, subgroup by treatment interaction, subgroup by visit interaction, and 3-way interaction of treatment, subgroup and visit.

The treatment-emergent injection site reaction and hypersensitivity reaction will be analyzed by a logistic regression model including terms of treatment, subgroup, treatment by subgroup interaction. All data regardless of IP use will be used for this analysis.

The negative binomial regression model specified in Table 6.6 with additional terms of subgroup, treatment by subgroup interaction will be used for the subgroup analysis of overall hypoglycemia event rate while on IP.

The interaction effects (3-way for MMRM and 2-way for ANCOVA/logistic regression model/negative binomial regression model) will be evaluated using a significance level of 0.10, unadjusted. If the interaction effect is significant ($p < 0.10$), separate analysis without the terms related with the subgroup will be performed for each subpopulation.

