6.13. Subgroup Analyses

6.13.1. Subgroup Analyses for HbA1c

The following subgroups will be analyzed for HbA1c if there are sufficient numbers of patients per group (for example, at least 10% in each group):

- age (<65 versus ≥ 65 years and <75 vs. ≥ 75 years and <65, ≥ 65 to <75, ≥ 75 to <85, ≥ 85 years)
- hemoglobin A1c stratum ($\leq 8\%$ vs. $> 8\%$)
- sex (male vs. female)
- body mass index (<25 vs. ≥ 25 , and <30 vs. ≥ 30 kg/m² and <35 vs. ≥ 35 kg/m²)
- duration of diabetes (using the median as the cut-off)
- race
- ethnicity
- country
- region
- baseline 1-hour PPG excursion (\leq baseline median, $>$ baseline median)
- baseline 1-hour PPG (PPG ≤ 180 mg/dl, > 180 mg/dl)

- baseline 2-hour PPG excursion (\leq baseline median, $>$ baseline median)
- baseline 2-hour PPG (PPG \leq 180 mg/dl, $>$ 180 mg/dl)
- type of basal insulin during the lead-in period (glargine vs. degludec)
- prandial insulin dosing plan (carbohydrate counting or pattern adjustment)
- number of prandial doses at study entry ($<$ 3 vs. \geq 3)
- sodium-glucose co-transporter 2 inhibitor treatment

Analyses for HbA1c and change from baseline in HbA1c will be performed using an MMRM model that includes the same fixed effects given for the primary analysis model plus factors of subgroup, 2-way interaction of subgroup and treatment, 2-way interaction of subgroup and visit, and 3-way interaction of treatment, visit and subgroup. The interaction of subgroup and treatment at the primary endpoint will be evaluated to assess the treatment by subgroup interaction. When analyzing HbA1c stratum as a subgroup the baseline HbA1c will be not be included as a covariate to avoid confounding. The subgroup interaction effect will be evaluated using a significance level of 0.10, unadjusted.

Additional subgroup analyses may also be performed.

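### SAP 6.12.7.1 judges antibody effect modification in the HbA1c and insulin-dose MMRMs by the three-way visit term, which tests change between visits and not modification at Week 26

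*SAP*

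**What the plan says.** SAP 6.12.7.1 plans subgroup analyses of selected efficacy and safety variables, which "will be performed by the TEADA status during the analysis period of Visit 2 to Visit 801". For HbA1c and for insulin dose it extends the MMRM with subgroup, subgroup-by-treatment, subgroup-by-visit and the treatment-by-subgroup-by-visit term. It then fixes the term to be judged: "The interaction effects (3-way for MMRM and 2-way for ANCOVA/logistic regression model/negative binomial regression model) will be evaluated". The criterion is that the interaction effects "will be evaluated using a significance level of 0.10, unadjusted". If p<0.10, "separate analysis without the terms related with the subgroup will be performed for each subpopulation". The section names no contrast at Week 26.

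SAP Table 6.2 gives the post-baseline observations for both MMRMs as "Visits 11, 13, 15, and 18 prior to discontinuation of IP", which the Protocol's Schedule of Activities places at Weeks 4, 8, 12 and 26.

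For the other HbA1c subgroups, SAP 6.13.1 adds the same terms to the same model but applies a different rule: "The interaction of subgroup and treatment at the primary endpoint will be evaluated to assess the treatment by subgroup interaction". Protocol 10.3.5.2 agrees: "The interaction of subgroup and treatment at the primary endpoint (Week 26) will be evaluated to assess the treatment by subgroup interaction". The HbA1c endpoint is the change to Week 26. The insulin-dose endpoint (SAP Table 4.1, objective 10) is "Change from baseline in total, basal and prandial insulin dose and prandial/total insulin dose ratio at Week 26".

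**The concern.** Because the model already holds the subgroup-by-treatment term, the three-way term carries only what is left: differences between visits in the treatment-by-TEADA effect. Its null hypothesis is that this effect is the same at all four visits, whether zero or not. The plan uses it both as the test of effect modification and as the trigger for the separate analyses.

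Two errors follow. A modification that is sustained from early on through Week 26 can pass unnoticed, and a non-significant result may be read as showing that antibodies do not alter the treatment effect. Conversely, a modification seen early and gone by Week 26 can trigger the separate analyses although nothing differs at the endpoint. The SAP gives no reason for treating TEADA differently from the subgroups in 6.13.1.

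**Working it through.** **Inputs from the documents.** 284 completers per arm, SD 1.1 and margin 0.4 (SAP 5.2); interaction tests two-sided at 0.10 (SAP 6.1); four post-baseline visits (SAP Table 6.2).

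**Assumptions not in the documents.** TEADA prevalence 5% to 50%; a modification of 0.4 HbA1c points; the visit SDs and correlations listed below.

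**1. The plan's own power figure.** SE = 1.1 × √(2/284) = 0.0923. Power = Φ(0.4/0.0923 − 1.96) = Φ(2.37) = 99.1%. This agrees with the stated 99%, so the SD and sample size are used as the plan uses them. The plan gives no power for the interaction test.

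**2. What each test examines.** Let δ₄, δ₈, δ₁₂, δ₂₆ be the difference in treatment effect between TEADA-positive and TEADA-negative patients at each visit.
- Three-way term: null δ₄ = δ₈ = δ₁₂ = δ₂₆, with 3 df.
- Week 26 contrast: null δ₂₆ = 0, with 1 df.

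If all four δ are equal, the noncentrality of the three-way test is 0 and it rejects at 10%, whatever the size of δ, the prevalence or the correlation.

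**3. Constant modification of 0.4.** With prevalence p in both arms, SE of the Week 26 contrast = 1.1 × √(2 × [1/(284p) + 1/(284(1−p))]). For p = 0.3 this is 1.1 × √(2 × [1/85.2 + 1/198.8]) = 0.201. Power ≈ Φ(0.4/0.201 − 1.645) = 63%.

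| Prevalence | SE | Week 26 contrast | Three-way test |
|---|---|---|---|
| 5% | 0.424 | 25% | 10% |
| 10% | 0.308 | 37% | 10% |
| 20% | 0.231 | 54% | 10% |
| 30% | 0.201 | 63% | 10% |
| 50% | 0.185 | 70% | 10% |
| 10% v 20% by arm | 0.272 | 43% | 10% |
| 20% v 40% by arm | 0.211 | 60% | 10% |

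In SD units 0.4/1.1 = 0.36, so the same figures hold for insulin dose if its modification is 0.36 SD. The documents give no dose SD.

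**4. Modification that varies over visits.** The three-way power comes from the noncentral chi-square with 3 df. Fifteen covariance structures were used: visit SDs of 0.5/0.65/0.8/1.1, 0.7/0.85/1.0/1.1 or 1.1 throughout, each crossed with compound symmetry (correlation 0.5, 0.7 or 0.8) or decaying correlation (0.8 or 0.9 per 4 weeks).

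| Modification at Weeks 4/8/12/26 | Prevalence | Three-way test | Week 26 contrast | Three-way rejects more often |
|---|---|---|---|---|
| 0.1/0.2/0.3/0.4 | 30% | 29–67% | 63% | 3 of 15 |
| 0.2/0.3/0.4/0.4 | 30% | 23–58% | 63% | 0 of 15 |
| 0.1/0.25/0.4/0.4 | 30% | 40–89% | 63% | 10 of 15 |
| 0/0.1/0.2/0.4 | 30% | 38–87% | 63% | 9 of 15 |
| 0/0.1/0.2/0.4 | 10% | 22–54% | 37% | 8 of 15 |
| 0.4/0.3/0.2/0 | 30% | 38–87% | 10% | 15 of 15 |
| 0.4/0.3/0.2/0 | 10% | 22–54% | 10% | 15 of 15 |

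The late-emerging pattern (0/0.1/0.2/0.4) and the fading pattern (0.4/0.3/0.2/0) give identical three-way results because they differ only by a reversal of sign and a constant, which the term cannot see. One has the full modification at Week 26 and the other has none.

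**5. Simulation check.** 10,000 trials, 30% prevalence, SD 1.1, exchangeable correlation 0.7, three-way against contrast: constant 0.4, 10% v 63%; no modification, 10% v 10%; fading, 71% v 10%.

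**The case against.** The strongest reply has four parts.

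- **The Week 26 question is inferred.** Section 6.12.7.1 sits under safety and names no time point. No objective asks about effect modification by TEADA, and the Week 26 rule in 6.13.1 and Protocol 10.3.5.2 covers listed subgroups that do not include TEADA. Antibodies accrue over time, so an interest in change over visits is defensible. It stands that no rule is broken outright, and for insulin dose those sections are only an analogy. But both endpoints are defined at Week 26, and a test of change over visits still does not show whether modification exists there.
- **A constant modification is the least plausible pattern.** All patients use insulin lispro until randomization, and HbA1c takes time to respond, so a full 0.4 points by Week 4 is unlikely. This stands: the 10% figure is a limiting case. When the modification builds up, the three-way test has real power, sometimes more than the contrast. There is no general loss of power; the fault is the null hypothesis.
- **Little depends on it.** The interaction model is fitted in any case, and a non-significant test withholds only the separate refits. This stands and limits the severity.
- **A 0.10 trigger on a descriptive contrast is awkward.** TEADA status is determined partly after randomization, and moving the test to Week 26 does not cure that. This stands, and is why the estimate and CI should be reported whatever the p-value.

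**Conclusion.** The concern holds. As written, the test and the trigger for the HbA1c and insulin-dose analyses by TEADA status address change between visits, not modification at Week 26. That follows from the model terms alone and needs no assumption.

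The size depends on assumptions. With 0.4 points of modification, 284 per arm and SD 1.1, a constant modification is flagged 10% of the time, against 25% to 70% for the Week 26 contrast. A modification gone by Week 26 is flagged in 22% to 54% of trials at 10% prevalence and 38% to 87% at 30%, against 10%. For modification that builds up, either test may have more power, depending on trajectory and covariance.

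The scope is narrow: an exploratory, unadjusted analysis; the other TEADA subgroup models use the two-way term; H1 to H4 are untouched. The change should be made, but it is not critical.

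**What to change.** In SAP 6.12.7.1, for the HbA1c and insulin-dose MMRMs:

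- evaluate the treatment-by-TEADA contrast at Week 26 (Visit 18) at the 0.10 level, and use it as the trigger for the separate analyses;
- report its estimate and CI whatever the p-value;
- keep the three-way term as a description of change over time;
- state that TEADA status draws on samples from Visit 2 through Visit 801, so partly after randomization and partly after Week 26, and that the contrast is therefore descriptive.

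No change to the PPG excursion model is proposed here. The cost is a few sentences in the SAP and one contrast from a model already planned, with no new data.

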6.12.7.2. Anti-Insulin Lispro Antibody Return to Baseline

Any patient who develops a TEADA response at any time during the treatment period that has not returned to baseline at Visit 801 should undergo follow-up for antibodies to insulin lispro for a maximum of 6 months after Visit 801 or until anti-insulin lispro antibodies return to baseline range, whichever occurs sooner. The analyses for return to baseline will only include patients meeting this antibody follow-up entry criteria. Return to baseline (RBL) is defined as

- CCI [REDACTED]
- CCI [REDACTED]

Reasons for discontinuation from the antibody follow-up at Visit 802 and 803 will be summarized by the randomized treatment groups. No treatment comparison will be conducted.

Duration of exposure to IP will be summarized by treatment groups. Only descriptive statistics: n, mean, SD, median, minimum, maximum, and sum (that is, total patient-years of exposure), will be provided.

The number and percentage of patients whose anti-insulin lispro antibody levels meet the RBL criteria will be summarized by visit (Visit 802, and 803).

For the patients participating in the insulin antibody follow up, a summary of HbA1c, the insulin dose (prandial, basal, and total daily insulin dose), vital signs, body weight, AEs, and concomitant medications reported during the immunogenicity follow-up period will be summarized by randomized treatment group. The summary will include descriptive statistics and no statistical test will be performed for treatment comparison.

A scatter plot using the antibody percent binding at the last visit in the immunogenicity follow-up period as X-axis and the HbA1c value at the same visit as Y-axis will be generated. A similar scatter plot with total daily dose as Y-axis will also be generated.

6.12.8. Patient Narratives

Patient narratives will be provided for all patients in the study who experience any of the following “notable” events prior to data cutoff for the submission:

- deaths
- serious adverse events
- discontinuations from study (or study drug) due to AEs
- pregnancy

A list of patients who meet the criteria for narratives will be provided.

6.13. Subgroup Analyses

6.13.1. Subgroup Analyses for HbA1c

The following subgroups will be analyzed for HbA1c if there are sufficient numbers of patients per group (for example, at least 10% in each group):

- age (<65 versus ≥ 65 years and <75 vs. ≥ 75 years and <65, ≥ 65 to <75, ≥ 75 to <85, ≥ 85 years)
- hemoglobin A1c stratum ($\leq 8\%$ vs. $> 8\%$)
- sex (male vs. female)
- body mass index (<25 vs. ≥ 25 , and <30 vs. ≥ 30 kg/m² and <35 vs. ≥ 35 kg/m²)
- duration of diabetes (using the median as the cut-off)
- race
- ethnicity
- country
- region
- baseline 1-hour PPG excursion (\leq baseline median, $>$ baseline median)
- baseline 1-hour PPG (PPG ≤ 180 mg/dl, > 180 mg/dl)

- baseline 2-hour PPG excursion (\leq baseline median, $>$ baseline median)
- baseline 2-hour PPG (PPG \leq 180 mg/dl, $>$ 180 mg/dl)
- type of basal insulin during the lead-in period (glargine vs. degludec)
- prandial insulin dosing plan (carbohydrate counting or pattern adjustment)
- number of prandial doses at study entry ($<$ 3 vs. \geq 3)
- sodium-glucose co-transporter 2 inhibitor treatment

Analyses for HbA1c and change from baseline in HbA1c will be performed using an MMRM model that includes the same fixed effects given for the primary analysis model plus factors of subgroup, 2-way interaction of subgroup and treatment, 2-way interaction of subgroup and visit, and 3-way interaction of treatment, visit and subgroup. The interaction of subgroup and treatment at the primary endpoint will be evaluated to assess the treatment by subgroup interaction. When analyzing HbA1c stratum as a subgroup the baseline HbA1c will be not be included as a covariate to avoid confounding. The subgroup interaction effect will be evaluated using a significance level of 0.10, unadjusted.

Additional subgroup analyses may also be performed.

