6.1. General Considerations

Statistical analysis of this study will be the responsibility of Eli Lilly and Company (hereafter Lilly). Any change to the data analysis methods described in the protocol will require an amendment ONLY if it changes a principal feature of the protocol. Any other change to the data analysis methods described in the protocol, and the justification for making the change, will be described in this SAP and/or in the clinical study report (CSR). Additional exploratory analyses will be conducted, as deemed appropriate.

Statistical analyses for Japan are described in [Appendix 2](#). Statistical Analyses for the Maximum Extended Enrollment (MEE) Addendum are described in [Appendix 3](#).

For purposes of analysis, the following populations are defined in [Table 6.1](#):

Table 6.1. Patient Populations

Population	Description
Entered	All patients who give informed consent.
Enrolled	All patients who receive at least 1 dose of open-label insulin lispro in the 8-week lead-in period.
Randomized	All patients who are randomly assigned to study treatment at Visit 8. Treatment group will be defined on the basis of the treatment the patients are assigned.
Safety	All randomized patients who receive at least 1 dose of the randomly assigned investigational product (IP). Treatment group will be defined on the basis of the treatment the patients are assigned.
Completer	Patients included in the randomized population who have completed Week 26 of study treatment without permanent discontinuation of IP. Treatment group will be defined on the basis of the treatment the patients are assigned.
Per Protocol	Patients included in the randomized population who have completed Week 26 of study treatment without permanent discontinuation of IP and without significant protocol deviations through Week 26 that would significantly impact the primary objective. Treatment group will be defined on the basis of the treatment the patients actually receive.

Unless otherwise stated, the efficacy analyses will be conducted on the Randomized Population, and the safety analyses will be conducted on the Safety Population.

The primary analysis is for the treatment period through Week 26.

Unless otherwise noted, all tests of treatment effects will be conducted at a 2-sided alpha level of 0.05, and CIs will be calculated at 95%, 2-sided. All tests of interactions between treatment groups and other factors will be conducted at a 2-sided alpha level of 0.10.

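### SAP 6.13.1 tests three continuous modifiers of the HbA1c effect only as median splits; a prespecified continuous interaction alongside would be a cheap gain if the modification is graded

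*SAP*

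**What the plan says.** SAP 6.13.1 lists "duration of diabetes (using the median as the cut-off", and splits "baseline 1-hour PPG excursion" and "baseline 2-hour PPG excursion" into values at or below versus above the baseline median. The model is the primary MMRM "plus factors of subgroup, 2-way interaction of subgroup and treatment, 2-way interaction of subgroup and visit, and 3-way interaction of treatment, visit and subgroup", and the subgroup-by-treatment contrast is read at the primary endpoint. On the threshold: "The subgroup interaction effect will be evaluated using a significance level of 0.10, unadjusted". SAP 6.1 supplies the sidedness: "All tests of interactions between treatment groups and other factors will be conducted at a 2-sided alpha level of 0.10".

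Protocol 10.3.5.2 says the subgroups serve "to evaluate consistency of treatment effects on the primary efficacy measure". It has the same cut for duration ("Duration of diabetes (using the median as the cut-off") but lists the two excursions with no cut; the SAP added the median there.

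Both documents allow further subgroup analyses, but neither names one with a continuous modifier. Neither gives an interaction size, a modifier distribution or a power for these tests. All three variables exist as continuous values. The excursions come from timed serum glucose in the mixed-meal test (Protocol 9.1.4.4). Diabetes duration comes from the diagnosis date on the case report form (SAP Table 6.3).

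**The concern.** A median split treats a patient just above the cut like one at the extreme. When the split variable is the modifier in an interaction test, the usual cost of dichotomising falls on the power of that test. These analyses are meant to judge consistency of effect, and a weak test can make a non-significant interaction look like consistency.

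The baseline excursion is also a natural modifier to examine, since the product rationale (Protocol 3.1 and 3.2) is better early postprandial control. What is at stake is how well the trial could detect or rule out a gradient of HbA1c benefit across these three variables.

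**Working it through.** **Inputs.** SD 1.1%, 568 completers (284 per group), margin 0.4%, true difference 0 (Protocol 10.1, SAP 5.2); 2-sided 0.10 for interactions (SAP 6.1, 6.13.1). Gradient and modifier shape are assumptions, varied below.

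**The plan's own figure first.** SE of the treatment difference = 1.1 × √(2/284) = 0.0923. Power = Φ(0.4/0.0923 − 1.96) = Φ(2.37) = 99.1%, matching the stated figure of more than 99%.

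**Interaction tests.** Let b be the change in treatment effect per SD of the modifier.

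- Continuous test: SE(b) = 2 × 1.1/√568 = 0.0923, so λ = b/0.0923.
- Median split: each half has 142 per arm, so the between-half difference in treatment effect has SE = 4 × 1.1/√568 = 0.185. Under a linear gradient its noncentrality is ρλ, where ρ is the correlation of the modifier with its own median split.
- Power = Φ(λ − 1.645) + Φ(−λ − 1.645), with ρλ replacing λ for the split.

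ρ is 0.798 for a normal modifier, 0.866 uniform, 0.719 lognormal (log-scale SD 0.5) and 0.693 exponential. Information kept is ρ²: 64%, 75%, 52% and 48%.

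| b (% HbA1c per SD) | Continuous power | Split power, normal | Loss, normal (points) | Loss, uniform | Loss, lognormal | Loss, exponential |
|---|---|---|---|---|---|---|
| 0.103 | 30% | 23.0% | 7.0 | 4.8 | 9.4 | 10.1 |
| 0.128 | 40% | 29.9% | 10.1 | 6.9 | 13.7 | 14.8 |
| 0.152 | 50% | 37.1% | 12.9 | 8.7 | 17.6 | 19.1 |
| 0.200 | 70% | 53.5% | 16.5 | 10.7 | 23.4 | 25.5 |
| 0.230 | 80% | 63.3% | 16.7 | 10.5 | 24.3 | 26.8 |
| 0.270 | 90% | 75.5% | 14.5 | 8.7 | 22.3 | 25.1 |
| 0.304 | 95% | 83.6% | 11.4 | 6.4 | 18.6 | 21.3 |
| 0.367 | 99% | 93.6% | 5.4 | 2.6 | 10.3 | 12.4 |

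Under normality the loss peaks at 16.8 points. At b = 0.05, λ = 0.54 and power is about 15% against 13%, a loss of about 2 points.

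Simulation with a normal modifier (ordinary least squares, 4,000 runs per setting) agrees: 50% against 37% at b = 0.15, 71% against 54% at 0.20, 85% against 70% at 0.25. Under the null both tests reject about 10% of the time.

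**The same in between-half terms (normal modifier).** The halves differ by d = 2√(2/π) × b = 1.596b.

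| d | Split | Continuous |
|---|---|---|
| 0.1% | 15% | 18% |
| 0.2% | 29% | 39% |
| 0.3% | 49% | 65% |
| 0.4% | 70% | 86% |

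**If the truth is a step.** For a step at percentile p ≥ 0.5, compare the step's correlation with each form of the modifier.

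- Normal: φ(z)/√(p(1−p)) for the continuous value against (1−p)/√(p(1−p)) for the split. They are equal where φ(z) = 1 − p, at about p = 0.62. By symmetry the split wins between about the 38th and 62nd percentiles.
- Exponential: the numerators are −(1−p)ln(1−p) and (1−p), equal at p = 1 − 1/e = 0.63. The split wins for any step below that.
- Sizes (simulated, normal): a step at the median gives the split 49% against 37% at d = 0.3, and 69% against 53% at d = 0.4. A 0.4% step at the 75th percentile gives 28% for the split and 39% for the continuous test.

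**Not modelled.** Borrowing across visits in the MMRM and covariate adjustment raise power for both forms but leave the efficiency ratio unchanged.

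**The case against.** The strongest case against is that this exchanges one assumed shape for another. The documents do not say whether any modification is graded or stepped, and over a wide middle range of step locations the split is the better test. A reader might infer that the continuous test is better except for a step exactly at the median; the working shows otherwise. This objection stands, and it is why the continuous test should sit beside the split and not replace it.

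Second, a reader might infer that the plan loses a fixed 10 to 16 points of power. It does not: that range rests on a gradient and a modifier shape that neither document gives. Between-half differences of 0.2 to 0.4% are also large where the whole margin is 0.4% and the planned overall difference is zero. At 0.1% both tests are nearly powerless and only about 3 points apart. This stands as a limit on how firmly the size can be stated.

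Third, these are consistency checks over 17 listed factors, unadjusted and outside the graphical testing scheme, with no power claimed. The product rationale is tested directly in H2 and H3, where baseline enters as a covariate (SAP 6.11.2). A median cut also meets, by construction, the SAP's condition of enough patients per group (10% is its example). All true, and it keeps the severity low. But the group-size condition explains a convenient cut for display; it is no reason to omit a continuous test.

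**Conclusion.** The concern holds as a conditional efficiency point. The three modifiers are tested only as median splits, no continuous interaction is prespecified, and no reason is given for the cuts.

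Under a linear gradient in a near-normal modifier, with SD 1.1%, 568 completers and 2-sided alpha 0.10, the cost is roughly 10 to 17 points where the continuous test would have about 40 to 95% power. It is about 2 to 7 points at gradients of 0.05 to 0.10% per SD, and about 15 to 27 points for a strongly right-skewed (exponential) modifier. Such skew is a possible shape for diabetes duration, but that is an assumption. For a step near the middle of the distribution the order reverses.

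A reader might take this as a threat to the trial's conclusions. The documents do not support that: the primary and multiplicity-adjusted tests do not use these splits. This is a cheap improvement of low severity.

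**What to change.** In SAP 6.13.1, before unblinding, add a second prespecified model for diabetes duration, baseline 1-hour PPG excursion and baseline 2-hour PPG excursion. Use the same MMRM with the continuous value and its interactions with treatment, with visit and with treatment-by-visit. Test the covariate-by-treatment slope at Week 26 at 2-sided 0.10. Report the estimated treatment difference at the 25th, 50th and 75th percentiles, giving the actual value at each. Keep the median-split analysis and its test alongside. Leave the age, BMI, HbA1c-stratum and 180 mg/dL cuts as they are.

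The cost is SAP wording and three more model fits on data already collected. The added test assumes linearity and is less sensitive to a step near the median, which the retained split covers. Three more unadjusted tests at 0.10 add 3 × 0.10 = 0.3 expected false positives when there is no modification, so the SAP should say that the two results for each variable are read together.
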